#### **4.2 Reporting**

Each participant will be observed and queried in a nonspecific fashion at each contact during the study for any new or continuing symptoms since the last contact. All adverse events will be reported on the appropriate electronic Case Report Form (eCRF). Details will include the type of event, date of onset, duration, intensity, causality relationship to the study drug(s) (if applicable), and outcome. Wherever possible, a diagnosis rather than symptom(s) will be reported.

If an adverse event should occur, every attempt will be made to obtain as much information as possible about event evaluation and outcome. Documents of this follow-up will be maintained with the patient's study records.

If a serious adverse event occurs, the treatment will be interrupted or discontinued at the physician investigator's discretion.

All protocol deviations will be reported to the investigator and the Institutional Review Board (IRB).

All adverse events will be reported to the IRB. All serious adverse events will be reported immediately to the IRB and the FDA (if applicable).

Endpoints will be adjudicated by the Principal Investigator. A written report detailing the endpoint adjudication will be provided by the Principal Investigator.

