#### 3.2.1 Research Design:

We propose a double-blinded, randomized, cross-over intervention study consisting of a moderate-intensity motor training circuit of gait-related upright motor control activities. We will also assess whether the addition of tDCS augments the training-related gains. Effects of training (and tDCS) on walking function, balance, strength, and spasticity will be assessed to determine whether there is preliminary evidence of efficacy of this approach.

**Stratified randomization:** To ensure equivalence of baseline data between groups, stratified randomization will be used. We have shown that persons with SCI who are ambulatory may be classified into one of two groups, with “**less impaired**” participants having lower limb motor scores of >15 for one leg and ≥10 for the other leg; participants not meeting this criteria are classified as “**more impaired**”. To ensure equivalent distribution of more- and less-impaired participants between groups, individuals will be stratified into one of these two strata based on the above criteria, with randomization to groups within each stratum.

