#### Schedule of Events:

[figure not shown]
Individuals will be asked to participate in the study over two, 5 consecutive day periods. Following completion of the fifth day, participants will be asked to take 2 weeks off before returning to the lab to repeat the intervention schedule but in the opposite group in which they originally participated (i.e. MT-only to MT+tDCS; MT+tDCS to MT-only). A detailed schedule of events including testing and intervention timing is provided in Figure 1.

**Figure 1.** Timing of intervention and outcome measures.

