- Motor training activities consist of dynamic exercises involving concentric and eccentric muscle contractions. This type of training may increase the mechanical forces placed on muscles and connective tissues of the lower extremities beyond that which participants may be accustomed. As a result, participants may experience signs and symptoms of delayed onset muscle soreness (DOMS) within the first 24-48 hours of training, the severity of which should lessen over the course of the training period. Participants' perceived severity of DOMS will be assessed prior to each session using a 1-10 verbal pain scale. Ratings of 8 or higher will result in a cancellation of that session. Participants will be instructed to take the day off, rest, and return for the next scheduled session. Participants will be assessed for pain/swelling of the lower limbs and joints prior to each training session and any abnormalities will be referred appropriately for medical management.
- There may be risks associated with blood tests. Taking blood may cause discomfort, bruising and, very rarely, infection where the needle goes into the skin. Participants may also experience dizziness, nausea, or fainting during blood draws. Participants will be instructed to inform the attending phlebotomist drawing the blood or other member of the study team if they are not feeling well while blood is being taken or at any time after blood has been taken.

Unanticipated Adverse Device Effect – any serious adverse effect on health or safety or any life-threatening problem or death caused by, or associated with, a device, if that effect, problem, or death was to previously identified in nature, severity, or degree of incidence in the investigational plan or application (including a supplementary plan or application), or any other unanticipated serious problem associated with a device that relates to the rights, safety, or welfare of participants.

Related or possibly related to the research: - an event is related to the research if, in the opinion of the Principal Investigator, it could not have been produced by the participant's clinical condition or environment, follows a known pattern of response to intervention, disappears or decreases with reduction in dose or cessation of intervention and/or recurs with re-exposure and/or it was more likely than not to be the result of the collection/disclosure of identifiable private information in the research and/or the interventions used in the research.

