### **6.1 Statistical Assumptions**

All data will be managed using Microsoft Excel and analyzed using SPSS. Descriptive statistics, including means, standard deviations and 95% confidence intervals of the pre-post change for each condition will be calculated for all measures. The baseline characteristics of the participants assigned to the 2 intervention groups will be compared using ANOVA and Chi-square analysis. The change from Baseline test (day 1) to Persistence test (day 5) for the two intervention groups will be compared using repeated measures ANOVA followed by pair-wise contrasts between the two groups. Pair-wise t-tests with Bonferroni correction for multiple comparisons will be used to evaluate within-day change for each of the 3 intervention days. We will identify the effect size and 95% confidence interval associated with effects to identify the outcome measures that are most sensitive to change following intervention with MT-only and MT+tDCS. We will also assess variables associated with responsiveness to intervention, using logistic linear regression to identify the variables that are most strongly associated with change in our primary outcome measure of walking function. Where significant pre/post differences exist among the primary outcome measures and blood serum concentrations of BDNF, Pearson correlation coefficients will be calculated to determine the strength of any relationship that might exist between measures of walking function and changes in BDNF concentration.

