### **8.0 Study Medication/Device/Intervention/Other Procedure Details**

Blinding: Assessors will remain blinded to participant group allocation throughout the duration of the study.

Assignment of Study Intervention: To ensure equivalence of baseline data, stratified randomization will be used to ensure equal distribution of more- and less-impaired participants between groups.

Dosing and Treatment: Participants will participate in a total 1x2-hour baseline testing session, 3x1-hour MT or MT+tDCS sessions, and 1x1hour follow-up testing session over 5 consecutive days. MT activities will take approximately 18 minutes to complete.

Identity of Medication/Device/Treatment: tDCS will be delivered using a Soterix Medical, Inc. 1x1 tDCS device.

Unblinding Procedures: Data will remain blinded throughout participant enrollment and testing. Interim data analyses will not be performed for this study. Data will be unblinded by [name] upon completion of all evaluations for all study participants.

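### By the visits the text describes, adverse events are actively solicited for about 15 to 16 days after the last session of period 1 but only about 1 day after the last session of period 2.

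*Combined protocol and SAP*

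**What the plan says.** Section 4.2 (Reporting) ties the collection of adverse events to contacts: each participant is to be "queried in a nonspecific fashion at each contact during the study for any new or continuing symptoms since the last contact". It does not define a contact, and it does not say when collection ends for a participant.

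The contacts themselves have to be read from the schedule. Section 8.0 gives each period one baseline session, then "3x1-hour MT or MT+tDCS sessions, and 1x1hour follow-up testing session over 5 consecutive days". Section 6.1 fixes the ends of the period by referring to "The change from Baseline test (day 1) to Persistence test (day 5) for the two intervention groups". Training therefore falls on Days 2 to 4. The Schedule of Events in Section 3.2.1 says what follows period 1: "Following completion of the fifth day, participants will be asked to take 2 weeks off before returning to the lab". The schedule is then repeated in the other condition. The text describes no contact after Day 5 of the second period.

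Section 4.1 names risks that may appear with a delay. It says participants may have "delayed onset muscle soreness (DOMS) within the first 24-48 hours of training", and for blood sampling it says: "Taking blood may cause discomfort, bruising and, very rarely, infection where the needle goes into the skin".

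**The concern.** A query about symptoms since the last contact reaches back only as far as the previous visit, and only if another visit follows. After period 1 another visit does follow, so the period 2 baseline query picks up events during the break, by recall. After period 2 the text describes no later visit, so the Day 5 query is the last one.

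Three things are at stake:

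- Each participant is observed for different lengths of time under the two conditions, so a within-person reading of adverse events does not compare like with like.
- Every event in the break attaches to whichever condition came first, because it is the only one the participant has received.
- Events that emerge after the final visit, or after someone leaves at the end of period 1, are recorded only if the participant volunteers them. Section 4.2 asks for the duration and outcome of each event, yet an event still present at the final Day 5 has no planned contact at which to complete those fields.

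**Working it through.** **Inputs**

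- Visits per period: 1 baseline, 3 training, 1 follow-up (Section 8.0).
- Baseline on Day 1 and persistence test on Day 5 (Section 6.1).
- Break of two weeks after Day 5 of period 1 (Schedule of Events).
- 35 enrolled, 15% attrition, 30 needed for analysis (Section 6.2).
- Four blood samples per participant: Day 1, Day 2 twice, Day 5 (Section 3.2.3 and Appendix I).

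**Reproducing the plan's own figure.** 1 + 3 + 1 = 5 days, which matches the stated period length. The last training session is Day 4. The plan states no figure for adverse-event follow-up, so that has to be derived.

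**Solicited follow-up after the last session** = day of the last scheduled query that can cover it, minus day of the last session.

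- Period 1, two weeks counted from Day 5 to the return visit: return on Day 5 + 14 = 19, so 19 − 4 = 15 days.
- Period 1, 14 full days free of visits: return on Day 20, so 20 − 4 = 16 days.
- Period 2: 5 − 4 = 1 day.

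The ratio between periods is 15:1 to 16:1.

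**By condition rather than period.** Assume 30 completers, 15 days in period 1 and 1 day in period 2. The sequence ratio is not stated, so two splits are shown.

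| Completers per sequence | Person-days, condition given first to the larger (or equal) sequence | Person-days, other condition |
|---|---|---|
| 15 / 15 | 15×15 + 15×1 = 240 | 15×15 + 15×1 = 240 |
| 16 / 14 | 16×15 + 14×1 = 254 | 14×15 + 16×1 = 226 |

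By period, the totals are 30×15 = 450 person-days against 30×1 = 30. The large imbalance is between periods. Between conditions it vanishes with balanced sequences and is small with a mild imbalance.

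**Soreness.** If the 24 to 48 hours run from each session, the window after the last session (Day 4) runs from Day 5 to Day 6. The final visit of period 2 then falls at its start, leaving about 48 − 24 = 24 hours without a query. If the phrase means the start of training, the window falls on about Days 3 to 4 and is covered by visits.

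**Blood sampling.** The listed draws are 1 + 2 + 1 = 4, exactly one period's set; the same set in both periods would be 8. The period is not stated, so a draw on Day 5 of period 2 is possible but not established.

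**Withdrawals.** 15% × 35 = 5.25, so about 5 participants. This is an upper illustration of how many might leave after period 1, because the plan does not say when attrition occurs.

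**The case against.** The strongest reply is that the randomised cross-over already deals with the problem. Section 3.2.1 describes both orders, so each condition receives the long window in some participants and the short one in others. A reader might take the 15:1 ratio as a bias of MT+tDCS against MT-only. The documents do not support that: the person-day totals above are equal for balanced sequences, and Section 6.1 plans no formal comparison of adverse events between conditions. This part of the reply stands, subject to the unstated sequence ratio and to dropout not differing by sequence.

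A reader might also infer that late events are never collected. That is too strong:

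- Section 4.2 speaks of contacts, which could include a telephone call.
- Section 4.1 tells participants to report feeling unwell after a blood draw, with no time limit.
- Section 5.3 mentions a questionnaire that can bring in records of outside treatment.
- Section 4.4 promises safety monitoring for the whole trial, and Table 4 runs it to month 48.
- Figure 1, which holds the detailed schedule, is not available and might show a later contact.

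These points soften the wording but do not fill the gap. The blood-draw instruction is spontaneous reporting of one kind of event. The questionnaire has no stated timing and concerns treatment sought elsewhere. Section 4.2's promise to pursue details serves events already known. The general monitoring statements set no participant contact. The scalp check in Appendix A is made when stimulation ends, so it sees immediate effects only.

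The soreness argument also weakens. Section 4.1 expects severity to lessen as training proceeds, and its time window may refer to the start of training. At most a tail after the last session is missed. The soreness rating is made before each session, and it is unclear whether the Day 5 testing session counts. The limb pain and swelling check is tied to training sessions, so it is not scheduled after Day 4.

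Finally, it would be tempting to say that every participant has an unfollowed blood draw on the last day. With only four samples planned, that cannot be claimed.

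**Conclusion.** The point holds as a matter of unequal and incomplete solicitation. As the text stands, active enquiry covers about 15 to 16 days after the last session of period 1 and about 1 day after the last session of period 2, with no scheduled query for anyone who leaves after period 1.

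The consequence is likely under-recording of late events in period 2 under both conditions, together with unequal within-person windows. A treatment bias would need unbalanced sequences or dropout that differs by sequence, and the documents establish neither.

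This rests on three assumptions: that contacts are the visits described in the text, that Figure 1 shows no later one, and that the two-week break is kept as written. Because the stated rule and schedule produce the inequality themselves, it is more than a missing detail. It is a low-cost improvement and does not threaten the primary analysis.

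**What to change.** In Section 4.2, state what counts as a contact and define the adverse-event window for each period as running from the first session to one brief telephone contact. Existing staff would make that call at the same fixed interval after Day 5 of each period, also for participants who withdraw. The call should ask about soreness, the scalp, the blood-draw site where relevant, and any other symptom.

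If the interval is k days after Day 5, follow-up after the last session becomes 1 + k days in both periods. The 30 completers then contribute 30 × (1 + k) person-days to each condition whatever the sequence split. The interval should be long enough to pass 48 hours after the Day 4 session (k of at least 1) and short enough for the period 1 call to fall within the break.

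Tabulate adverse events by condition within these equal windows. List events reported between the period 1 call and the period 2 baseline visit separately.

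Cost: at most 2 × 35 = 70 short calls, a sentence or two in Section 4.2, and slight burden for participants and the coordinator. Treatment, eligibility, endpoints and sample size are unchanged.

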#### **4.3 Potential Side Effects**

Potential side effects have been listed under *Anticipated Adverse Events* in Section 4.1.

#### **4.4 Safety**

This study will be conducted in accordance with the principles of Good Clinical Practice as outlined in the Declaration of Helsinki and the International Conference on Harmonization.

All efforts will take place to ensure patient safety. Each participant will be monitored for safety throughout the trial utilizing clinical evaluations and laboratory markers.

Laboratory markers and/or clinical evaluations that are out of normal range will be recorded as adverse events and reviewed with the investigator.

SAE's noted to be study drug/device/research intervention related will be reported as appropriate and [study drug/device/ intervention is to be discontinued per the decision of the investigator].

All participants will be triaged to the appropriate medical care based on investigators decision upon review of abnormal events.

### **5.0 Data Management**

Following completion of the consenting process (including informed consent and Authorization for Use/Disclosure of PHI) and it has been determined that the participant meets all of the inclusion and none of the exclusion criteria, enrollment will occur and data collection will commence.

#### **5.1 Case Report Forms**

Hospital, office, and research records for any admission or visit (including admission notes, discharge notes, operative reports, test results, and lab reports) are considered source documentation and will be collected and reviewed to confirm clinical events and may be utilized for data analysis. Data will be collected on all participants via an eCRF. The CRF will contain no participant names. The participant code field will be a patient study number, numbered sequentially as entered into the electronic database. A separate master code list will be constructed by the investigator/study coordinator that will list the patient name with the designated participant code. This list will be maintained in a password protected file to which only investigators involved in the project will have access.

Upon completion of data collection, an eCRF will be printed for the participant, signed by a Principal Investigator, and filed in the participant's research chart.

#### **5.2 Database**

Data will be collected and maintained in electronic form by [name]. Data entry, development of the primary database, and all statistical analyses will be the responsibility of [name]. The electronic database will be backed up per institutional guidelines.

#### **5.3 External Documentation:**

During administration of the patient questionnaire, if it is identified that a participant sought treatment from a source outside of the Hulse Spinal Cord Injury Laboratory after enrollment into the protocol, additional data will be obtained from external physician offices or hospitals to document and verify events. All data will be entered onto the follow-up eCRF.

#### **5.4 Quality Control**

[name] will fulfill the responsibilities identified in their standard operating procedures. These responsibilities include collecting and tracking data forms and instituting quality control measures for data entry verification and study compliance. He will request further documentation such as physician and/or procedure notes when complications are observed and reported. [name] will also be responsible for auditing the database and confirming the overall integrity of the data. He will ensure that all information pertaining to significant new developments and unanticipated adverse events are provided to the appropriate regulatory authorities, the Investigators, and to the IRB.

Monitoring of the study will be conducted at regular intervals in order to monitor study conduct and maintain Good Clinical Research Practice. These inspections are conducted in order to verify adherence to the protocol and the completeness and accuracy of the data being entered into the eCRF.

### **6.0 Statistical Considerations**

*The study protocol must provide the research methodology with sufficient detail to answer the following questions:*

- 1) *Is the sample size and nature appropriate for the goals of the study?*
- 2) *For placebo-controlled studies, is there adequate justification for a placebo arm; is the duration of the intervention limited to that which is minimally necessary; is there adequate monitoring of participants receiving placebo?*
- 3) *Are there defined endpoints for discontinuing experimental treatment in the event of a worsening condition?*
- 4) *Is the proposed research design and statistical treatment of data appropriate and sufficient?*
- 5) *Does the proposed research carry enough likelihood of yielding valid information to warrant the participation of Shepherd Center patients?*

### **6.1 Statistical Assumptions**

All data will be managed using Microsoft Excel and analyzed using SPSS. Descriptive statistics, including means, standard deviations and 95% confidence intervals of the pre-post change for each condition will be calculated for all measures. The baseline characteristics of the participants assigned to the 2 intervention groups will be compared using ANOVA and Chi-square analysis. The change from Baseline test (day 1) to Persistence test (day 5) for the two intervention groups will be compared using repeated measures ANOVA followed by pair-wise contrasts between the two groups. Pair-wise t-tests with Bonferroni correction for multiple comparisons will be used to evaluate within-day change for each of the 3 intervention days. We will identify the effect size and 95% confidence interval associated with effects to identify the outcome measures that are most sensitive to change following intervention with MT-only and MT+tDCS. We will also assess variables associated with responsiveness to intervention, using logistic linear regression to identify the variables that are most strongly associated with change in our primary outcome measure of walking function. Where significant pre/post differences exist among the primary outcome measures and blood serum concentrations of BDNF, Pearson correlation coefficients will be calculated to determine the strength of any relationship that might exist between measures of walking function and changes in BDNF concentration.

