A preponderance of the evidence suggests that corticospinal drive is increased by **combining** moderately intense motor training with stimulation of supraspinal centers. This notion is supported by research demonstrating that intensive motor training aimed at increasing corticospinal drive improves muscle activation and walking function.[15] Furthermore, non-invasive brain stimulation has been shown to improve lower extremity strength, lower-limb control, gait, and balance.[16-19] Cortical stimulation with repetitive transcranial magnetic stimulation (rTMS) has been associated with improved walking function in persons with SCI [20], although this form of stimulation has inherent drawbacks that limit its use in clinical settings. An alternative to rTMS is transcranial direct current stimulation (tDCS), which is a low-risk, non-invasive brain stimulation technique involving low-intensity currents delivered to the motor cortex and aimed at modulating cortical excitability. tDCS is affordable and lacks many of the drawbacks associated with rTMS, making it a more clinically accessible technology. Emerging studies in persons with stroke have combined tDCS with moderately intense motor training and have demonstrated increased dorsiflexor control,[16] quadriceps strength,[17, 18] and balance.[17] tDCS may also have the capacity to modulate excitability of spinal networks and to decrease spasticity.[21, 22]

Based on the evidence described above, we put forward two primary goals of the proposed project: *1) determine whether a moderate-intensity training program designed to increase control of gait-related movements can improve functional and neurophysiologic measures, and 2) determine whether training-related responses are larger when training is augmented with cortical stimulation to increase supraspinal drive.*

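### The trial is a two-period crossover, but Section 6.1 does not state that the MT+tDCS versus MT-only comparison is within-person, uses both periods, or adjusts for period

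*Combined protocol and SAP*

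**What the plan says.** Section 3.2.1 sets the design: "We propose a double-blinded, randomized, cross-over intervention study". The Schedule of Events gives two 5-day periods, and between them "participants will be asked to take 2 weeks off before returning to the lab to repeat the intervention schedule but in the opposite group". Each completer therefore supplies two Day 1 to Day 5 changes, one under each condition.

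The analysis is described only in Section 6.1. For the comparison of conditions it states: "The change from Baseline test (day 1) to Persistence test (day 5) for the two intervention groups will be compared using repeated measures ANOVA". Contrasts of one group against the other come next. It also promises "95% confidence intervals of the pre-post change for each condition" as descriptive output, and it tests baseline characteristics between the two intervention groups with ANOVA and chi-square. Section 6.2 plans 15 participants in each group, 30 in all, and enrols 35 to allow for 15% attrition.

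No section names the repeated factor in the ANOVA, says whether one or both periods are analysed, or mentions a period or sequence term.

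**The concern.** Section 1.0 lists, as the second of two primary goals, to "determine whether training-related responses are larger when training is augmented with cortical stimulation to increase supraspinal drive". In a crossover this question is answered by the difference between a participant's two changes. The repeated factor in 6.1 could be condition, which gives a paired analysis. It could equally be time, with group as a between-person factor, which treats the MT-only and MT+tDCS records as different people.

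The surrounding text does not settle the matter. In a completed crossover both conditions contain the same people, so testing their baseline characteristics against each other makes sense only for parallel groups or for the two sequences. The sample size is also built per group.

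At stake are the standard error and power of the tDCS comparison. Because more than one analysis fits the text, the choice could also be made after the data are seen. Even the paired reading has no period term, so a difference in gains between the two training weeks would go into the error or, with unequal sequences, into the estimate.

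**Working it through.** **Inputs**
- Completers: 30 (Section 6.2).
- Significance level: 0.05 (Section 6.2). Sidedness is not stated; two-sided is assumed.
- Difference between conditions: 0.69 SD of the change score. In 6.2, 0.69 is the pre-post effect of training alone, so its use as the tDCS increment is an assumption.
- Within-person correlation of the two changes (rho): not given; 0, 0.3 and 0.5 are shown.
- Period effect: not given; 0, 0.345 and 0.69 SD lower gain in the second period are shown. The last equals the whole assumed training effect and is extreme.

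**1. The plan's own figure.** With 15 participants and an effect of 0.69, a paired t-test of pre-post change has power 0.81 one-sided and 0.70 two-sided, so the stated 0.8 is reproduced only one-sided. For 15 v 15 independent participants the SE is sqrt(2/15) = 0.365 SD, and power at 0.69 is 0.58 one-sided and 0.45 two-sided. The between-group 0.8 is thus not reproduced at 0.69; 6.2 assumes an additive or larger tDCS effect but gives no number for it. That is a separate matter for 6.2. What counts here is that the calculation contains no within-person correlation: it is an independent-groups calculation.

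**2. Benchmark: crossover analysis with a period term.** SE = sqrt(2(1 - rho)/30), with 28 degrees of freedom:
- rho 0: sqrt(2/30) = 0.258
- rho 0.3: sqrt(1.4/30) = 0.216
- rho 0.5: sqrt(1/30) = 0.183

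Noncentral-t power at 0.69 is 0.73 / 0.87 / 0.95.

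**3. Paired analysis without a period term.** With no period effect, power is the same as the benchmark (0.87 at rho 0.3). A period effect P shifts the within-person difference by -P in one sequence and +P in the other. With 15:15 sequences the estimate is unbiased, but the apparent variance of the difference rises from 2(1 - rho) to about 2(1 - rho) + P² x 30/29. At rho 0.3:
- P = 0.345: 1.4 + 0.119 x 30/29 = 1.523; apparent SE sqrt(1.523/30) = 0.225; simulated power 0.85 v 0.87.
- P = 0.69: 1.4 + 0.476 x 30/29 = 1.892; apparent SE sqrt(1.892/30) = 0.251; simulated power 0.79 v 0.87.

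With unequal sequences the estimate is biased by P x (n1 - n2)/30. At 17:13 this is 0.345 x 4/30 = 0.05 SD or 0.69 x 4/30 = 0.09 SD, with a sign that depends on which sequence is larger. Simulated type I error stayed between 2% and 5.3%.

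**4. Both periods pooled as independent groups.** The analysis uses sqrt(2/30) = 0.258 as its SE whatever rho is, while the true SE is that in step 2. Simulation with no period effect gives:

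| rho | SE used / true SE | Power, pooled | Power, crossover | Type I error, pooled |
|---|---|---|---|---|
| 0 | 1.0 | 0.75 | 0.73 | about 5% |
| 0.3 | 1.2 | 0.79 | 0.87 | about 2% |
| 0.5 | 1.4 | 0.82 | 0.95 | about 0.7% |

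At rho 0 pooling loses nothing. With positive rho it is conservative and loses power.

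**The case against.** The best defence is that 6.1 already intends a paired analysis. The Schedule of Events uses group to mean condition, since participants return "in the opposite group in which they originally participated (i.e. MT-only to MT+tDCS; MT+tDCS to MT-only", and 6.1 itself speaks of each condition. If the outcome is the Day 1 to Day 5 change, a participant has one value per period, so condition is the natural factor to repeat. This stands as the likeliest reading, and under it the loss is small. It is not conclusive, because an ANOVA of raw scores by group and time would repeat over time instead.

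The stakes are also limited. Section 6.2 puts the main interest in training itself, and Section 3.2.1 aims "to determine whether there is preliminary evidence of efficacy of this approach". Section 8.0 rules out interim analyses and unblinds only after all evaluations, which narrows the room for a data-driven choice. It does not close it, because the analysis is still unspecified at unblinding.

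Stronger readings are tempting, but the documents do not support them:
- **Only the first period will be analysed, with power 0.45.** Nothing in 6.1 discards the second period; this would be an inference from the baseline tests and the sample-size text.
- **The plan inflates false positives.** Neither the paired nor the pooled analysis does so materially in the settings above.
- **Carryover is ignored.** The 2-week break is the design's provision for it.
- **Omitting stratum, or a rule for participants with one period, does serious harm.** Randomisation is stratified ("individuals will be stratified into one of these two strata based on the above criteria, with randomization to groups within each stratum"), but stratum cancels from the within-person difference in completers. Keeping five one-period participants moves the SE only from 0.216 to 0.211 at rho 0.3.

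**Conclusion.** The concern holds as a gap in specification. Section 6.1 does not match the crossover design: the within-person factor, the use of both periods and the period term are all unstated, and no other section supplies them.

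On the likeliest (paired) reading, omitting period costs nothing without a period effect, 0.02 of power at a moderate one and 0.08 at an extreme one, plus a small bias if the sequences end unequal. On the unpaired reading that the text also allows, power falls by 0.08 at rho 0.3 and 0.13 at rho 0.5, with an over-conservative test. These sizes rest on an assumed correlation, tDCS increment and period effect, none of which the documents give. The harm is lost precision and an open analysis choice, not a false claim of benefit. It merits correction because the comparison is a stated primary goal and the correction is nearly free.

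**What to change.** In Section 6.1, state that the MT+tDCS versus MT-only comparison uses each participant's Day 1 to Day 5 change from both periods, with condition as a within-person factor and period and sequence as fixed effects. Report the within-person difference with its 95% CI. Describe baseline characteristics by sequence instead of testing them between conditions. Settle this before the unblinding described in Section 8.0.

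Optional, with little gain: fit it as a mixed model that keeps participants with one period and includes impairment stratum.

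The cost is one paragraph, slightly more analysis work, and one degree of freedom for the period term (29 to 28 with 30 completers). No visits or participants are added.
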